5.5.13. Work Productivity and Activity Impairment (WPAI-D)

Definitions

The WPAI:D questionnaire is a validated short instrument that assesses impairment in work and other regular activities over the past 7 days. The WPAI yields four types of scores:

- 1. Absenteeism (work time missed)
- 2. Presenteeism (impairment at work / reduced on-the-job effectiveness)

- 3. Work productivity loss (overall work impairment / absenteeism plus presenteeism)
- 4. Activity Impairment.

The first three scores will be derived only for respondents who are working (should be missing for non-working), but the last score is applicable for all respondents. WPAI scores are expressed as percent impairment, with higher values indicating greater impairment. A score cannot be calculated if there is a missing response to the corresponding item.

The questions of the WPAI-D are:

Q1 = currently employed

- Q2 = hours missed due to problems associated with depression
- Q3 = hours missed other reasons
- Q4 = hours actually worked
- Q5 = degree depression affected productivity while working
- Q6 = degree depression affected regular activities

The 4 scores are calculated as follows:

- 1. Absenteeism: Q2*100/(Q2+Q4)
- 2. Presenteeism: Q5*10
- 3. Work productivity loss: 100*[Q2/(Q2+Q4) + (1 Q2/(Q2+Q4)) * Q5/10]
- 4. Activity Impairment: Q6*10

Analysis Methods

See section 5.5.1 for the analysis of the 4 WPAI scores.

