6.3. Appendix 3 Demographics and Baseline Characteristics

6.3.1. Demographics

The following demographic variables will be summarized by intervention group:

Continuous Variables	Summary Type
Age (years)	Descriptive statistics (N, mean, standard deviation [SD], median and range [minimum and maximum]
Weight (kg) at baseline	
Categorical Variables	
Age (18-64 years, >=65 years)	
Sex (male, female, undifferentiated)	
Japanese Ancestry (Yes, No)	
Occupational/employment status (full time employed, part time employed, casually employed, sheltered work, employed, but currently on sick or disability leave, unemployed due to depression, but seeking work, unemployed for reasons unrelated to depression, but seeking work, unemployed due to depression, but not seeking work, unemployed for reasons unrelated to depression, but not seeking work, retired, housewife or dependent husband/partner, student, no information available)	Frequency distribution with the number and percentage of participants in each category.

The following variables will be summarized for female participants by intervention group:

Continuous Variables	Summary Type	
Average length of menstrual cycle (days)	Descriptive statistics (N, mean, standard deviation	
Time from last menstrual period to date of assessment	[SD], median and range [minimum and maximum]	
Categorical Variables		
Subject's childbearing potential (of childbearing potential, permanently sterilized, postmenopausal, not applicable)	Frequency distribution with the number and percentage of participants in each category.	
Did menstrual period occur since last assessment (Yes, No)		

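### The WPAI missing-item rule in SAP 5.5.13 can delete a work-productivity-loss score that the SAP's own formula fixes at 100, and 'working' is left undefined

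*SAP*

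**What the plan says.** SAP 5.5.13 derives four WPAI scores from six questions. The relevant ones are "Q1 = currently employed", "Q2 = hours missed due to problems associated with depression", Q4 (hours worked) and "Q5 = degree depression affected productivity while working". The recall period is 7 days.

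- Absenteeism uses Q2 and Q4 only.
- Presenteeism uses Q5 only.
- Work productivity loss uses Q2, Q4 and Q5.
- Activity impairment uses Q6 and applies to all respondents.

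Two sentences decide when a score exists. One limits eligibility: "The first three scores will be derived only for respondents who are working (should be missing for non-working". The other is the missing-item rule: "A score cannot be calculated if there is a missing response to the corresponding item". Neither mentions an employed person who worked no hours in the week.

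All four scores are analysed under SAP 5.5.1 as change from baseline with baseline as covariate, by an observed-case MMRM and by ANCOVA on LOCF data.

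**The concern.** An employed participant who was off work all week because of depression has the worst work outcome the scale can record. The formula already fixes that person's score at 100 without help from Q5. A rule that makes the score missing because Q5 is blank discards a known value over an item that cannot change it.

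The plan foresees people in this position: SAP 6.3.1 lists "employed, but currently on sick or disability leave" as an employment category. Missingness would then be caused by the outcome itself, at the bad end of the scale. Return to work is also one of the changes that a work-productivity endpoint is meant to detect.

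**Working it through.** The SAP states no numerical WPAI result, so there is no figure to reproduce. The check evaluates its formula and then follows the result through its rules.

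**1. Formula (SAP 5.5.13).** With A = Q2/(Q2+Q4), work productivity loss = 100 × [A + (1 − A) × Q5/10].

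**2. Full absence through depression: Q2 > 0, Q4 = 0.** A = Q2/Q2 = 1, so the score is 100 × [1 + 0 × Q5/10] = 100. Evaluated at Q2 = 8, 20 and 40 hours and every Q5 from 0 to 10, it is 100.0 each time. Absenteeism is 100 × Q2/(Q2+0) = 100.

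**3. Near neighbour: Q2 = 39, Q4 = 1.** A = 0.975. The score is 97.5 at Q5 = 0, 98.75 at Q5 = 5 and 100 at Q5 = 10. One hour worked with Q5 answered keeps a near-maximal score; zero hours with Q5 blank gives none.

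**4. No hours missed through depression and none worked: Q2 = Q4 = 0.** A is 0/0, so absenteeism and work productivity loss are properly missing.

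**5. What happens to the person in step 2.** It depends on two things the documents leave open.

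| Meaning of 'working' | Q5 | Work productivity loss | Absenteeism |
|---|---|---|---|
| Employed (Q1 = yes) | answered | 100 | 100 |
| Employed (Q1 = yes) | blank | missing (missing-item rule) | 100 |
| Worked in the past 7 days | either | missing (eligibility sentence) | missing (eligibility sentence) |

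The score survives in only one of the three rows. That Q5 is blank at zero hours is inferred from its label and from Protocol 8.1.2.6, which defines presenteeism as impairment during work.

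**6. Effect in the SAP 5.5.1 models when the score is removed.**
- Full absence at baseline: no baseline score, so no change in work productivity loss at any visit. A fall from 100 to, say, 30 (100 − 30 = 70 points) would not enter the model for this score.
- Full absence arising later: the participant is left out of the MMRM at that visit. Under LOCF an earlier score is carried forward if there is one, and it cannot be worse than 100.

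**7. Size, by illustration only.** Let s be the share of employed respondents who are fully absent with Q5 blank, and m the mean of the rest. The mean at a visit should be 100s + (1 − s)m but is reported as m, a shortfall of s(100 − m). Both inputs are assumed. With s = 5% and m = 60 the shortfall is 0.05 × 40 = 2 points; with s = 30% and m = 40 it is 0.30 × 60 = 18 points. These are errors in one arm's mean at one visit.

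A between-arm difference is distorted only if the shortfalls differ. With m = 50 in both arms, 10% absent in each gives 5 − 5 = 0. With 10% against 20%, the means should be 55 and 60, but both are reported as 50, so a 5-point difference is reported as none.

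**The case against.** The strongest reply is that the decisive step is not in the documents. The missing-item rule removes the score only if Q5 is blank, and neither document reproduces the questionnaire or gives a skip instruction. If Q5 is answered and 'working' means employed, the existing formula returns 100 and nothing is lost. This stands: a reader might infer that the SAP certainly deletes the score of every fully absent employee, and the documents do not support that. It does not rescue the text, because the plan should not depend on how an item that cannot affect the score is filled in.

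A reader might also infer that return to work vanishes from the WPAI analysis. It does not if 'working' means employed: absenteeism needs only Q2 and Q4, scores full absence as 100 and goes into the same models. Activity impairment is kept for everyone, and SAP 5.5.12 separately analyses the SDS days-lost items. Only on the narrower reading of 'working' is absenteeism lost as well.

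A third tempting reading is that the treatment comparison is biased by a known number of points. No such figure can be derived. The documents do not say how many participants will be fully absent, and the sick-leave category shows neither a count nor how such people answer Q1 to Q5. The illustration concerns means at one visit, not the planned between-arm difference in change from baseline.

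Finally, the eligibility sentence might be meant to exclude people on leave. If so, the SAP should say so, because it would then exclude full absence through the disease under study from a score of work lost to that disease.

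**Conclusion.** Wrong as written, within narrow limits. The formula settles the score at 100 when Q2 > 0 and Q4 = 0, while the missing-item rule, which has no exception, can set it to missing. This holds if Q5 is blank for such participants, which is likely but inferred. If 'working' means having worked that week, work productivity loss and absenteeism are both lost whatever happens to Q5.

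Where scores are lost, the loss is informative, and neither the observed-case MMRM nor LOCF repairs it. The comparison is affected to the extent that full absence differs between arms; the size cannot be computed from the documents. The reach is one of four WPAI scores, or two on the narrower reading, among employed participants, for an endpoint that Protocol section 3 lists under other secondary and SAP 5.5 treats as supportive. The primary and key secondary endpoints are unaffected.

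**What to change.** In SAP 5.5.13, define 'working' as Q1 = yes and add a derivation rule to this effect:

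> If Q1 = yes, Q2 > 0 and Q4 = 0, absenteeism and work productivity loss are 100 irrespective of Q5; presenteeism is missing if Q5 is missing. If Q2 + Q4 = 0, absenteeism and work productivity loss are missing.

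Both parts are needed. The derivation rule alone could still be overridden by the eligibility sentence, and the definition alone leaves the missing-item rule in force. Nothing is imputed, since 100 is what the SAP's formula gives for any Q5. If Q5 turns out to be answered for these participants, the rule changes no score.

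The cost is a short text change and a corresponding line in the derivation program, with no new data. It should be settled before the WPAI analysis is run.

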5.6. Tertiary/Exploratory Endpoint(s) Analysis

Not applicable.

5.7. (Other) Safety Analyses

All safety analyses will be based on the safety analysis set (based on actual intervention received), unless otherwise specified.

For all continuous safety variables, descriptive statistics by intervention group will include the N, mean, standard deviation, median, minimum, and maximum. Categorical variables will be summarized by intervention group using frequency counts and percentages.

5.7.1. Extent of Exposure

The number and percentage of participants who receive each study agent within a study intervention will be summarized.

Descriptive statistics for duration of study intervention (N, mean, SD, median, and range (minimum, maximum)) will be summarized.

Study intervention duration is defined as (date of last dose of study intervention – date of first dose of study intervention) +1.

A frequency distribution of the total number of dosing sessions of intranasal study medication will be presented.

Starting dose for a participant is defined as the first dose taken after randomization. Modal dose for a participant is defined as the most frequently taken dose by a participant. Mean dose of a participant is calculated as the sum of doses during the phase divided by the total number of days exposed in the phase. The final dose is the last non-zero dose received during the phase. The calculation of mean, modal and final dose will exclude days off study drug.

Descriptive statistics (N, mean, SD, median, minimum and maximum) of starting dose, modal dose, mean dose and final dose will be presented for quetiapine XR and oral AD. For esketamine a frequency distribution will be presented.

The number (%) of participants with a dose adjustment/dose not administered will be summarized for each study agent within a study intervention. Reasons for dose adjustments/doses not administered will also be summarized.

5.7.2. Adverse Events

The verbatim terms used in the CRF by investigators to identify adverse events will be coded using the Medical Dictionary for Regulatory Activities (MedDRA). All AEs and special reporting situations, whether serious or non-serious, will be reported from the time a signed and dated ICF is obtained until completion of the participant's 2-week safety follow-up visit. Serious AEs, including those spontaneously reported to the investigator within 30 days after the last dose of study intervention, must be reported.

Any AE occurring at or after the initial administration of study intervention through completion of the participant's 2-week safety follow-up visit is considered to be treatment emergent. Serious AEs reported within 30 days after the last dose of study intervention are also regarded as treatment emergent. If the event occurs on the day of the initial administration of study intervention, and either event time or time of administration are missing, then the event will be assumed to be treatment emergent. If the event date is recorded as partial or completely missing, then the event will be considered to be treatment emergent unless it is known to be prior to the first administration of study intervention based on partial onset date or resolution date. All reported treatmentemergent adverse events will be included in the analysis. For each adverse event, the number and percentage of participants who experience at least 1 occurrence of the given event will be summarized by intervention group.

Summary tables, for the first 8 weeks and for the whole study, will be provided for treatmentemergent adverse events:

- AEs
- Serious AEs (SAEs)
- AEs leading to discontinuation of each study agent within a study intervention
- AEs by severity

- AEs by relationship to each study agent within a study intervention
- AEs leading to dose interruption/dose modification of each study agent within a study intervention.

In addition to the summary tables, listings will be provided for participants who:

- Had SAEs
- Had AEs leading to discontinuation of study intervention.

Incidence of treatment-emergent adverse events of special interest will be summarized, grouped in the following MedDRA-based categories: sedation, dissociation, suicidality, suggestive of abuse potential, cystitis, and hepatic impairment. See Appendix 8 for a list of adverse events in each category.

The number and percentage of participants taking concomitant medication for dissociation events (preferred term of Dissociation) at any time during each treatment phase will be provided.

A listing of participants who died will be provided.

5.7.3. Additional Safety Assessments

5.7.3.1. Clinical Laboratory Tests

Clinical laboratory tests will be displayed for the participants included in the safety analysis set.

Descriptive statistics (N, mean, SD, median and range) for observed values and changes from baseline will be provided for clinical laboratory tests (hematology, chemistry, and urinalysis) at each scheduled time point by intervention group.

Clinical laboratory tests that meet the criteria for markedly abnormal will be listed by participant for each phase. The incidence of treatment-emergent markedly abnormal laboratory values that occurred at any time during the treatment phase will be presented. Clinical laboratory test values will be considered treatment-emergent markedly abnormal (TEMA) using the criteria defined by the sponsor listed in Attachment 10. The identification of TEMA laboratory values is based on the post-baseline value being out of range while the baseline value is either missing or within the range given in Attachment 10. If post-baseline laboratory results are above the upper limit and the baseline value is below the lower limit, then the post-baseline abnormality will also be considered TEMA. The same applies to the post-baseline value being below the lower limit.

The incidence of participants with ALT or AST values > 3*upper normal limit (ULN) will be presented. Additionally, incidence of hepatic toxicity (Hy's Law) defined as ALT or AST values > 3*ULN AND total bilirubin values > 2*ULN will be presented. Similar to the markedly abnormal analysis, only participants with baseline ALT or AST values \leq 3*ULN (AND baseline total bilirubin values \leq 2*ULN for hepatic toxicity) (or if the baseline value is missing) will be eligible for these analyses.

5.7.3.2. Vital Signs and Physical Examination Findings

Vital sign parameters weight, pulse, blood pressure (systolic and diastolic) and respiratory rate will be summarized at each assessment time point, including the change from baseline, will be summarized by intervention group.

In addition, descriptive statistics of pre-dose and post-dose pulse rate, blood pressure (systolic and diastolic) values and respiratory rate, and changes from pre-dose will be provided for each intranasal dosing day.

Abnormality criteria (based on criteria defined in the table below) will be applied to baseline and postbaseline values. For baseline values, increase or decrease criteria are not applied.

Postbaseline values will be considered TE if they meet both value and change criteria in the table below.

For criteria that do not include an increase or decrease from baseline:

- TE will be concluded if the postbaseline value is above the upper limit and the baseline value is below the upper limit (eg, Normal or Low). The same applies to the postbaseline value being below the lower limit with the baseline value being above the lower limit (eg, Normal or High).
- If the baseline value is missing, a postbaseline abnormality will always be considered as TE.

Incidence of treatment-emergent abnormal vital signs during intervention, as defined in the table below, will be summarized for participants who had a baseline assessment and at least 1 postbaseline assessment for that vital sign.

8			
	Post-baseline value outside of normal limit if:		
Vital Parameter	Abnormally low	Abnormally high	
Pulse (bpm)	A decrease from Baseline of ≥ 15 to a value ≤ 50	An increase from Baseline of ≥ 15 to a value ≥ 100	
Systolic BP (mmHg)	A decrease from Baseline of ≥ 20 to a value ≤ 90	An increase from Baseline of ≥ 20 to a value ≥ 180	
Diastolic BP (mmHg)	A decrease from Baseline of ≥ 15 to a value ≤ 50	An increase from Baseline of ≥ 15 to a value ≥ 105	
Respiratory rate (breaths per minute)	Any value < 10	Any value > 24	

Table: Treatment-Emergent Abnormality Categories for Vital Signs

BP = blood pressure; Baseline is defined in Section Error! Reference source not found..

The proportion of subjects who experienced treatment-emergent acute hypertension (systolic BP \geq 180 or diastolic BP \geq 110) at any time during each treatment phase will be summarized.

5.7.3.3. Electrocardiogram

For the scheduled time points the following items will be summarized:

- Was the ECG performed, Yes / No;
- Overall interpretation, Normal / Abnormal / Not evaluable;
- Clinically significant, Yes / No.

In case the interpretation is abnormal, the specification will be listed.

In case the abnormality is assessed to be clinically significant, the associated Medical History Condition and/or Adverse Event will be listed.

5.7.3.4. Nasal Examination

During the predose nasal examination the grade of the symptoms epistaxis, nasal crusts, nasal discharge and nasal erythema, scored as absent, mild, moderate or severe, will be summarized as frequency distributions. Comments to the symptom assessments will be listed.

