- ^f Must be performed prior to esketamine dosing in applicable participants (ie, randomly assigned to the esketamine arm).
- ^g The treatment continuation assessment will be performed on all participants who are taking study intervention (ie, both components of the randomized combination therapy) (see Section 4.1) and will be the basis for the decision to continue study intervention. If the study intervention is discontinued early, the CGI-C (ie, the basis of the treatment continuation assessment for the study interventions) will still be performed at follow-up visits; however, treatment decisions will be at the discretion of the investigator and not based on the criteria for the treatment continuation assessment.
- ^h Blood samples should be collected in fasting condition (at least 8 hours fasting, water is permitted). If clinically relevant abnormal results are found in hematology, chemistry, or urinalysis tests, tests should be repeated more frequently at the discretion of the investigator. Additionally, required laboratory tests as recommended in the respective SSRI/SNRI SmPC (or local equivalent, if applicable) should be performed.
- ¹ Urine pregnancy testing (at site/local) for women of childbearing potential. Counseling on pregnancy prevention will be provided at all visits, if applicable. Additional serum or urine pregnancy tests may be performed, as determined necessary by the investigator or required by local regulation, to establish the absence of pregnancy at any time during the participation in the study.
- ^j Vital signs: blood pressure, pulse/heart rate, respiratory rate.
- ^k At Week 32 and at the safety follow-up visit (no esketamine nasal spray dose), vital signs will be performed according to usual practice and nasal examination as described below will be performed.
- ¹ Visual inspection of nostrils, nasal mucosa, and throat for nasal erythema, rhinorrhea, rhinitis, capillary/blood vessel disruption, and epistaxis.

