8.2.1. Physical Examinations

Physical Examination

A physical examination will be performed at screening.

Body Weight and Height

Body weight will be measured as per the Schedule of Activities. Height will be measured at Screening.

Nasal Examinations

Nasal examinations (including the upper respiratory tract/throat) will be conducted by a qualified healthcare practitioner authorized by local regulation to conduct a physical examination. The objective of the examination at screening is to rule out any participants with anatomical or medical conditions that may impede drug delivery or absorption.

Subsequent examinations will only be performed in participants randomly assigned to the esketamine arm and will consist of a visual inspection of the nostrils, nasal mucosa, and throat for nasal erythema, rhinorrhea, rhinitis, capillary/blood vessel disruption, and epistaxis, and will be graded as follows: absent, mild, moderate, or severe.

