9.4.4. Safety Analyses

All safety analyses will be made on the Safety Population defined in Section 9.3.

Adverse Events

The verbatim terms used in the eCRF by investigators to identify AEs will be coded using MedDRA. Intervention-emergent AEs are AEs occurring or worsening in severity after the start of study intervention. All reported intervention-emergent AEs will be included in the analysis. For each AE, the percentage of participants who experience at least 1 occurrence of the given event will be summarized by intervention group. In addition, comparisons between intervention groups will be provided if appropriate.

Summaries, listings, datasets, or participant narratives may be provided, as appropriate, for those participants who die, who discontinue intervention due to an AE, or who experience a severe or a SAE. Adverse events reported occurring after study intervention discontinuation will be tabulated.

Intervention-emergent AEs of special interest will be summarized separately, grouped in the MedDRA based categories specified in Section 8.3.7.

Vital Signs

Descriptive statistics of pulse/heart rate, respiratory rate, and supine blood pressure (SBP and DBP) values and changes from baseline will be summarized at each scheduled time point. The percentage of participants with values beyond clinically important limits will be summarized.

Nasal Examination

Abnormalities observed during the targeted nasal examinations at screening and post-baseline will be summarized and listed by treatment group.

C-SSRS

Suicide-related thoughts and behaviors based on the C-SSRS will be summarized by study intervention in incidence and shift tables. Separate endpoints for suicidal ideation and suicidal behavior will be defined and summarized descriptively by study intervention. Missing scores will not be imputed.

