1. INTRODUCTION

This statistical analysis plan describes the definitions of analysis sets, derived variables, and statistical methods for all planned statistical analyses to be documented in the CSR for protocol 54135419TRD3013. Additional (abbreviated) SAPs will be developed for various supplementary and post-hoc analyses.

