6.3.2. Nasal examination

The following variables will be summarized for the nasal examination performed at screening by intervention group:

Categorical Variables	Summary Type
Condition (Structural/Functional Abnormalities, Septal Deviation, Signs of Infections, Obstruction/Functional Lesions, Other Findings)	Frequency distribution with the number and percentage of participants in each category.

The specifications of the conditions recorded will be listed.

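### SAP 5.7.3.4 plans graded nasal summaries only for predose examinations and leaves out two of the protocol's five graded signs, contrary to Protocol 9.4.4 and without declaring the change

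*SAP*

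**What the plan says.** Protocol 8.2.1 says that nasal examinations after screening are done only in the esketamine arm and look for "nasal erythema, rhinorrhea, rhinitis, capillary/blood vessel disruption, and epistaxis, and will be graded as follows: absent, mild, moderate, or severe".

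The Schedule of Activities for Weeks 9 to 32 (Protocol 1.3.2) marks a predose nasal examination at each maintenance dosing session. It also marks a nasal examination at Week 32, at the early study withdrawal visit and at the safety follow-up visit. For Week 32 and the safety follow-up, a footnote says that no esketamine is given and still requires the inspection: "nasal examination as described below will be performed". For participants who stop study intervention early, another footnote adds the safety follow-up assessments to their first 2-week follow-up visit.

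Protocol 9.4.4 sets out the analysis: "Abnormalities observed during the targeted nasal examinations at screening and post-baseline will be summarized and listed by treatment group". It has no predose limit.

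The SAP splits the work in two. SAP 6.3.2 handles screening: "The following variables will be summarized for the nasal examination performed at screening by intervention group". SAP 5.7.3.4 handles the rest: "During the predose nasal examination the grade of the symptoms epistaxis, nasal crusts, nasal discharge and nasal erythema" will be summarized as frequency distributions over the same four grades as the protocol, and comments will be listed. SAP Appendix 2, which records departures from the protocol's analyses, mentions only time to relapse.

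**The concern.** The SAP states in its introduction that it covers "statistical methods for all planned statistical analyses to be documented in the CSR for protocol 54135419TRD3013". An analysis missing from it therefore has no specification, even where the protocol has promised it in general terms.

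Two gaps follow from SAP 5.7.3.4 as worded. The terms do not match the examination that the protocol prescribes, and the examinations made without a dose fall outside the output. Neither gap is declared.

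Local nasal effects belong to the esketamine route, and this trial follows them for 32 weeks. The examinations without a planned summary are the last ones in completers and the post-treatment one in participants who stopped early, some of whom may have stopped for tolerability. A programmer following the SAP would produce a nasal table that is incomplete against the protocol, and a reader of the study report would not be told why.

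**Working it through.** No sample size, power or event figure is involved. The check compares two lists and then counts visits and sessions.

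**Signs**

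| Protocol 8.2.1 | SAP 5.7.3.4 | Match |
|---|---|---|
| epistaxis | epistaxis | by name |
| nasal erythema | nasal erythema | by name |
| rhinorrhea | nasal discharge | only if the two terms are equated |
| rhinitis | none | no summary planned |
| capillary/blood vessel disruption | none | no summary planned |
| none | nasal crusts | not in the protocol's list |

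With discharge read as rhinorrhea, 3 of 5 protocol signs are covered, 2 of 5 are not, and 1 term is added. By literal name, 2 of 5 are covered, 3 are not, and 2 terms are added. I use the reading more favourable to the SAP.

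**Examinations**

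- Screening: covered by SAP 6.3.2.
- Predose at dosing visits: covered by SAP 5.7.3.4, for its four terms.
- Week 32: no dose, not covered.
- Early study withdrawal: nasal examination marked in the schedule, no nasal session marked, not covered.
- Safety follow-up, including the first 2-week follow-up visit after early discontinuation: not covered. SAP 5.10 (follow-up phase) does not list nasal examination among its parameters.

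For participants dosed every 2 weeks, the schedule places the safety follow-up at Week 32, so these are one visit. For weekly dosing it falls at Week 33.

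The neighbouring SAP sections carry no such limit. Vital signs (5.7.3.2), ECG (5.7.3.3) and pregnancy tests (5.7.3.5) are all summarized at the scheduled or assessed time points.

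**Exposure already covered by predose examinations**

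- Sessions through Week 8: Days 1, 4, 8, 11, 15, 18, 22, 25, 29, 36, 43, 50 and 57, which is 13.
- Weekly maintenance, Weeks 9 to 31: 23 sessions. Total 13 + 23 = 36. The Week 31 predose examination follows 36 − 1 = 35 of them.
- Every-2-week maintenance, Weeks 10, 12, …, 30: 11 sessions. Total 13 + 11 = 24. The Week 30 predose examination follows 24 − 1 = 23 of them.

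These are full scheduled counts. A participant who moves between frequencies falls between 24 and 36. For a completer, the uncovered examinations add the effect of one further session, seen one to two weeks later.

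**The case against.** The case for leaving the SAP alone has four parts.

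1. **Adverse events catch what matters.** Protocol 8.2 requires clinically relevant changes to be recorded as adverse events, and SAP 5.7.2 counts events through the safety follow-up visit as treatment emergent. A reader might infer from SAP 5.7.3.4 that nasal findings at Week 32 and later are never reported. The documents do not support that: relevant findings enter the adverse event tables, and Protocol 9.4.4 still commits to post-baseline summaries and listings. What stands against this objection is that graded findings below the clinical-relevance threshold have no output. None of the special-interest categories in Protocol 8.3.7 and SAP Appendix 8 covers nasal events. An adverse event table also does not give the distribution of grades by visit.

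2. **The eCRF may explain the terms.** A reader might conclude that rhinitis and vessel disruption are collected and then discarded. That cannot be established, because the eCRF is not among the documents and the SAP's terms may simply mirror its fields. This objection stands. If it is the explanation, the mismatch lies between protocol and eCRF, and it still needs declaring.

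3. **Cumulative exposure is nearly all covered.** A reader might infer that cumulative nasal harm would be understated. The session counts do not bear that out for visit coverage, since predose examinations follow all but the last scheduled session. This also stands.

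4. **The protocol section is only a summary.** Protocol 9.4 leaves technical detail to the SAP. That allows the SAP to choose a display, but not to drop, without saying so, examinations that Protocol 9.4.4 includes.

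**Conclusion.** The point holds as a mismatch between SAP and protocol that should be corrected. As written, SAP 5.7.3.4 plans no summary for 2 of the 5 signs graded under Protocol 8.2.1. It plans no graded summary or listing of abnormalities for the nasal examinations at Week 32, early study withdrawal and safety follow-up. Both narrow Protocol 9.4.4, and Appendix 2 declares neither.

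The consequence is modest. It concerns descriptive safety reporting in one arm. There is no between-arm comparison of these grades after screening, because only esketamine participants are examined. No efficacy result, significance level or power is touched.

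The count of 2 assumes that discharge means rhinorrhea; by literal name it would be 3. The coverage conclusion takes the SAP's word predose at face value. Which signs were actually recorded cannot be settled without the eCRF.

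**What to change.** Reword SAP 5.7.3.4 so that it:

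- summarizes grades for every post-baseline nasal examination, whether or not a dose is given, including Week 32, early study withdrawal, safety follow-up and the first follow-up visit after early discontinuation;
- lists abnormalities from those examinations, as Protocol 9.4.4 promises, and not only comments;
- uses the five signs of Protocol 8.2.1, or gives an explicit mapping (for example, discharge to rhinorrhea), with crusts kept as an extra term if the eCRF collects it.

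Declare in Appendix 2 any protocol sign that the eCRF did not capture, and any visit deliberately left out. A shift table of worst post-baseline grade is optional; the protocol does not ask for it.

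The cost is one SAP paragraph, possibly a line in Appendix 2, and a small extension to an existing descriptive table and listing. It requires no new visit or examination.
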